Preliminary Studies: Numerous studies published by [name] and the collaborating research team involving MSM have informed the proposed research.^{58,66,70,71,124,149-156} The study team has successfully enrolled multiple cohorts of non-treatment seeking MSM in non-abstinence-based pharmacologic and behavioral trials with excellent participation in study visits, procedures, and retention rates.^{66,124,125,150} Our previous research has also demonstrated that reductions in substance use can result in parallel reductions in HIV sexual risk behaviors.^{66,71} **Table 1** lists relevant studies conducted by our group. **Project iN (intermittent naltrexone) study:** The current proposal logically builds on this pilot study establishing the feasibility, acceptability and tolerability of ION among 30 meth-using MSM without severe use disorders (ClinicalTrials.gov Identifier: NCT01723384). Preliminary data were extremely promising with a 61% screen to enroll rate, 95% retention rate and 93% study completion rate, suggesting that conducting a larger efficacy study on ION is feasible among meth-using MSM without severe use disorders. In addition, MSM in the trial reported high acceptability for the study procedures: most were satisfied /highly satisfied with the study (76%), were very likely to participate in a future study (71%), and were very likely to recommend the study to a friend (71%). No one in the study had stopped medications because of adverse events, suggesting that this intervention is tolerable in this population. This pilot was not powered to detect efficacy. We recognize the need for caution when interpreting results of pilot studies for hypothesis testing, as well as the controversy on estimating treatment effects from pilot studies.^{157,158} Nevertheless, specifying and testing analyses on meth use and sexual behaviors in the context of our pilot work is an important step in determining the applicability of our measures and analyses for a larger formal efficacy trial. In *exploratory, intention-to-treat (ITT) analyses*, we noted a point estimate consistent with a protective *signal* in favor of naltrexone, compared to placebo, on meth use (RR = 0.82).¹⁰⁹ While this was not statistically significant, we recognize that in small trials such as ours, type II error (i.e., false negatives) is a bigger concern due to small samples sizes, as opposed to type I error (i.e., false positives).¹⁵⁸ Hence, we interpret this result with caution. The study also found that meth-using MSM who used at least 1 day per week had significantly greater reductions in meth-using days when treated with ION, compared to placebo in a sub-group analysis (RR = 0.78).¹⁰⁹ Finally, we also found that ION participants had greater reductions in serodiscordant receptive anal intercourse (RR = 0.15) and serodiscordant condomless receptive anal intercourse (RR = 0.11), compared to placebo.¹⁰⁹ Participants also reported taking study drug 64% of the days that they craved meth or anticipated meth use. While this study drug compliance rate is better relative to our other pharmacotherapy trials with daily dosing, it still indicates a gap in compliance that can be enhanced with an adherence intervention, such as EMI. Hence, these findings support the *feasibility, acceptability, tolerability, and potential utility of ION to treat MSM who use meth and reduce HIV-related risks.*

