PrEP ART adherence by drug levels (HIV-), viral load (HIV+)		X		X		X
Study drug MEMS adherence monitoring		X	X	X	X	

*Confirmatory tests will be performed for reactive tests. S=Screening, E=Enrollment visit /Baseline, W=weekly, M = Month (M 3 = Final visit),

8.10 STANDARD CLINICAL PRACTICE: To what extent, if any, do the planned research procedures differ from the care that people would otherwise receive at this institution or the study site if not being done locally:

All participants will receive substance use counseling and psychotherapy for reducing methamphetamine use disorder. There is no FDA approval to use oral Naltrexone for reducing meth use disorder. This differs from the care that people would otherwise receive at the institution.

8.11 INSTRUMENTS: List all questionnaires, surveys, interview, or focus group guides that will be used for this study:

Table #4 provides a summary of the study measures:

TABLE 4: SUMMARY OF MEASURES

Data Source

Schedule

PRIMARY PREDICTOR VARIABLE

Trial arm (ION+EMI, placebo+EMI)

Randomization

En

OUTCOME VARIABLES

Primary biologic outcome

Urine samples: negative vs. positive for meth

Urine samples

En, Wkly

PrEP* and ART adherence

Lab specimens

En, M 1-3,

Behavioral outcomes^{201,202}

Total # of sexual partners, by partner HIV status; number of partners using Pre-Exposure Prophylaxis (PrEP); # of partners with undetectable viral load

ACASI

En, M 1-3,

Total # of condomless sex acts on/off PrEP/ART, by partner HIV status, PrEP status and viral load status

ACASI

En, M 1-3,

Reported days/episodes meth use¹¹⁶ timeline follow-back

ACASI; EMA

En, W, M 1-3,

Other substance use (opioids, alcohol, cocaine, marijuana, ecstasy, gamma-hydroxybutyrate, etc.)

ACASI;

En, M 1-3

Injecting behaviors: needle-sharing, sharing works

ACASI

En, M 1-3

Substance use treatment (outside study)	ACASI	En, M 1-3
Barratt's Impulsivity Scale ¹⁸⁶	ACASI	En, M 1-3
Substance use antecedences: Brief Substance Use Craving ¹⁷² ; Visual Analog Scale Craving Scores ¹⁷³ ; Daily Craving ¹⁷⁴ ; Affect, Mood ¹⁷⁵ ; Sexual Excitation Scale/Sexual Inhibition short form ¹⁸⁷ , Perceived Stress Scale ¹⁷⁶ , EMA Risk Antecedents ¹⁹⁷	ACASI; EMA	En, W, M 1-3, Daily

Additional covariates

Demographics (age, race, education, income)	ACASI	En
Brief Symptom Inventory ²⁰⁴ , Severity of Dependence ²⁰⁵	ACASI	En, M 1-3,

Study Drug, MEMs and EMA adherence

Timing of pill via MEMs cap openings	MEMS Caps	Daily

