Specific Aim 1: *To determine the efficacy of ION vs. placebo in reducing meth use, as determined by the proportion of meth-positive sweat patch tests.* As in our prior trial, a GEE Poisson model with robust standard errors will be used to compare weekly urine test results by treatment assignment; this provides easier-to-interpret risk-ratios²¹⁸ rather than odds-ratios. The treatment effect of ION vs. placebo will be modeled as linearly increasing and summarized by the between-group difference in means at 12 weeks, net of any baseline difference. *Minimum Detectable Effects (MDEs) with sample size:* Based on the prior trial (93% retention with an 8-week follow-up), we estimate that 90% of participants will be retained at 12 weeks, and within-subject correlation will be 0.45. Under these assumptions, the study sample of 60 participants will have 80% power in 2-sided tests with a type-I error rate of 5% to detect net between-group differences in the reduction in urine positivity of ~24 percentage points, equivalent to a relative rate reduction of 32%. We have observed similar reductions on meth use in ITT and sub-group analyses in prior trials.¹⁰⁹ Therefore, we believe that the reductions in meth use we are powered to detect in this aim are reasonable to anticipate. *In sensitivity analyses,* we will also evaluate between-group differences on changes in: 1) any meth-positive samples or self-report of meth use in timeline follow back; and 2) meth positivity from self-report only. Concordance of the urine testing, and self-reported measures will be examined using weighted Kappa and correlations. We recognize that meth use is a stigmatized behavior that may be underreported. Hence, in the event of discrepancies between urine test results and timeline follow back data on meth use, we will treat the urine test results as the gold standard. *Additionally, we will analyze participant's perception of whether the EMI prompts had effects on various HBM constructs and explore whether these moderate treatment effects on meth use.*^{119,120}

Specific Aim 2: *To determine the efficacy of ION vs. placebo in reducing meth-associated sexual risk behaviors.* We will use GEE Poisson models with robust standard errors to assess evidence that the intervention reduces HIV risk behaviors, including number of sex partners,

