- Students
- Staff of UCSF or affiliated institutions
- None of the above

11.6 * SPECIAL SUBJECT GROUPS: Check the populations that may be enrolled: (REQUIRED)

- Children / Minors
- Adult subjects unable to consent for themselves
- Adult subjects unable to consent for themselves (emergency setting)
- Subjects with diminished capacity to consent
- Subjects unable to read, speak or understand English
- Pregnant women
- Fetuses
- Neonates

Prisoners
 Economically or educationally disadvantaged persons
 None of the above

11.7 INCLUSION CRITERIA: Briefly describe the population(s) that will be involved in this study. Include anyone that data will be collected from or about (e.g. patients, healthy controls, caregivers, providers, administrators, students, parents, family members, etc.):

Inclusion Criteria: 1) cisgender male (male gender and sex assigned at birth); 2) age 18-70 years* (naltrexone's tolerability and safety has been demonstrated among older adults up to age 70^{166,167}); 3) self-reported condomless anal sex with men or missing PrEP or ART doses due to meth use in the prior three months while under the influence of meth; 4) self-reported meth use at least weekly; 5) positive meth sample via sweat patch or urine testing during screening; 6) mild, moderate, and severe meth use disorder as determined by DSM-V-SCID criteria; 7) interested in reducing meth use; 8) no current acute illness requiring prolonged medical care; 9) no chronic illness that is likely to progress clinically during trial; 10) able and willing to provide informed consent and adhere to visit schedule; 11) current CD4 count \geq 200 cells/mm³; or CD4 count of 100-199 cells/mm³ and HIV viral load $<$ 200 copies/mL (if living with HIV); 12) baseline CBC, total protein, albumin, glucose, alkaline phosphatase, creatinine, BUN, and electrolytes without clinically significant abnormalities as determined by study clinician in conjunction with symptoms, physical exam, and medical history.

11.8 EXCLUSION CRITERIA: List any exclusion criteria (e.g. reasons why someone would not be included in the study):

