**07/13/2021**

## Statistical Analyses

We will use generalized estimating equations (GEE) to estimate treatment effects on repeated study outcomes. Primary analyses will be by intention-to-treat (ITT). In prior trials, we had excellent visit retention and study completion. Nonetheless, in this high-risk population, missing data may be encountered. We will conduct sensitivity analyses imputing all missing urine samples as positive, adjusting for baseline correlates of missingness, and using inverse probability of censoring weights.

**Specific Aim 1:** *To determine the efficacy of ION vs. placebo in reducing meth use, as determined by the proportion of meth-positive urine tests.* As in our prior trial, a GEE Poisson model with robust standard errors will be used to compare weekly urine test results by treatment assignment; this provides easier-to-interpret risk ratios rather than odds ratios. The treatment effect of ION vs. placebo will be modeled as linearly increasing and summarized by the between-group difference in means at 12 weeks, net of any baseline difference.

**Minimum Detectable Effects (MDEs) with sample size:** Based on the prior trial (93% retention), we estimate that 90% of participants will be retained at 12 weeks, and within-subject correlation will be 0.45. Under these assumptions, the study sample of 54 participants will have 80% power in 2-sided tests with a type-I error rate of 5% to detect net between-group differences in the reduction in urine positivity of ~24 percentage points, equivalent to a relative rate reduction of 32%. We have observed similar reductions on meth use in ITT and subgroup analyses in prior trials. Therefore, we believe that the reductions in meth use we are powered to detect in this aim are reasonable to anticipate.

**Specific Aim 2:** *To determine the efficacy of ION vs. placebo in reducing meth-associated sexual risk behaviors.* We will use GEE Poisson models with robust standard errors to assess evidence that the intervention reduces HIV risk behaviors, including number of sex partners, and number of sex partners with whom meth is used.

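### Aim 1 justifies a 32% detectable reduction in urine positivity by pilot reductions of 18–22%, one of them in using days, and the day count collected weekly has no named analysis

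*SAP*

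**What the plan says.** The SAP (Statistical Analyses, Specific Aim 1) models the weekly positive/negative urine result with a Poisson GEE. The effect is linear in time and is read at week 12, net of baseline. The SAP states that "the study sample of 54 participants will have 80% power" to detect a net difference in "urine positivity of ~24 percentage points, equivalent to a relative rate reduction of 32" percent. It then supports that size with "We have observed similar reductions on meth use in ITT and subgroup analyses in prior trials" and concludes that an effect this large can fairly be expected. Protocol 11.3 makes the same argument with 60 participants.

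The pilot results are in Protocol 8.5:

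- The intention-to-treat RR was 0.82. It was not significant and is described only as an effect on meth use.
- The subgroup using at least one day a week had "significantly greater reductions in meth-using days when treated with ION, compared to placebo in a sub-group analysis (RR = 0.78").

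Protocol 8.13 summarises the two as reductions of 18%–22%.

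Table 4 (Protocol 8.11) lists "Reported days/episodes meth use" among the outcome variables, by timeline follow-back, at enrollment, weekly and monthly. Protocol 8.13 and 11.3 plan two sensitivity analyses that use self-report. One combines it with urine, and the other is "meth positivity from self-report only". The SAP contains neither.

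**The concern.** Two things are treated as alike that are not. First, 18–22% is smaller than 32% on any scale. Second, the only pilot result with a stated unit is a ratio of using days, whereas the detectable effect is a ratio of weekly positivity. A participant who cuts from five using days a week to four can remain positive every week, so a given percentage cut in days normally produces a smaller percentage cut in positivity.

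At stake is how Aim 1 will be read. If the drug did what the pilot suggested, the primary test would probably be null, after the plan had told readers that the detectable effect was in line with earlier experience. The measure on which the pilot found its significant meth-use result is collected weekly, but it has no named model. A day-count result shown after a null urine result would then look post hoc.

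**Working it through.** **Inputs from the documents.** "80% power in 2-sided tests with a type-I error rate of 5" percent; 54 participants (SAP) or 60 (Protocol 11.3); 2:1 allocation, so 36:18 of 54; within-subject correlation 0.45; linear effect read at week 12; pilot RRs 0.82 and 0.78.

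**Reference positivity.** 0.24 / 0.32 = 0.75, so the stated effect is 75% against 51%.

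**Reproducing the plan's figure.** Take 13 weekly measures (weeks 0–12) with exchangeable correlation 0.45. The variance factor for the week-12 difference is (1 − 0.45) × 144/182 = 0.435, and

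SE = √(0.435 × [p1(1−p1)/18 + p2(1−p2)/36]).

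At p1 = 0.75 and p2 = 0.51, SE = √(0.435 × [0.01042 + 0.00694]) = 0.0869. Then 0.24/0.0869 − 1.96 = 0.80, which is 78.9% power. The detectable effect at 80% power is 24.4 points at 54 participants and 23.1 at 60. The plan's 24 points reproduces.

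**Pilot ratios carried over to urine with no loss.**

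| Pilot RR | Difference | Power, N=54 | Power, N=60 |
|---|---|---|---|
| 0.78 | 0.75 × 0.22 = 16.5 points | 48% | 52% |
| 0.82 | 0.75 × 0.18 = 13.5 points | 35% | 38% |

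This does not hinge on the variance model. The most favourable alternative tried (mean of 12 weeks, adjusted for baseline) still needs 20.0 points at 54 and 18.9 at 60.

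**Pilot ratios read as ratios of using days.** The assumptions, none of them in the documents, are independent days with use probability p, a urine detection window of w days, and 75% reference positivity. Solve 1 − (1−p)^w = 0.75, then recompute with p × RR. For w = 2, p = 0.50. With RR 0.78 this falls to 0.39, and positivity becomes 1 − 0.61² = 62.8%, a drop of 12.2 points.

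| Window | RR 0.78: drop (power, N=54) | RR 0.82: drop (power, N=54) |
|---|---|---|
| 2 days | 12.2 points (30%) | 9.8 points (21%) |
| 3 days | 11.0 points (25%) | 8.8 points (18%) |
| 7 days | 9.8 points (21%) | 7.8 points (15%) |

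The share of the no-loss difference that survives runs from 7.8/13.5 = 58% to 12.2/16.5 = 74%. If use is strongly clustered (negative binomial with dispersion k = 1), the drops are 4.9 and 3.9 points, about 30% survives, and power is 7–8%.

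**Would a day-count analysis do better?** Apply the same linear model to log counts, with SE = √(0.435 × [v1/18 + v2/36]) and v = 1/mean + 1/k. The documents give neither the mean nor the overdispersion. Assuming 1.4–3 days a week and anything from Poisson to k = 1, power at 54 is 16–58% for RR 0.78 and 12–41% for RR 0.82.

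**The case against.** The best defence has four parts.

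- *Urine is a reasoned primary.* The protocol says meth use is stigmatised and may be underreported, and it makes urine the reference standard. This stands, and nothing here displaces urine.
- *Only one pilot figure is documented as days.* The 0.82 has no unit. The protocol says the prior trial used the same GEE approach, so it may be a urine ratio. This also stands. For the 0.82 only the size mismatch is certain.
- *The shortfall is mainly one of size.* On urine with no loss of scale, power is already only 35–48%. This is correct, and it is why the justification must be corrected whatever one thinks of day counts.
- *Modelling days does not restore power.* At 12–58% it does not. It would give an estimate on the pilot's own scale.

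Some stronger readings are tempting. A reader might infer that the trial analyses nothing but a yes/no urine result, or that no planned analysis could show a fall in use. The documents do not support either. The protocol plans self-report comparisons, although as positivity, and both documents commit in general terms to GEE for repeated outcomes, of which days of use is a listed one. What is missing is a named day-count model.

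A reader might also infer that a pilot-sized effect would almost vanish in urine. That rests on detection window, frequency and clustering, which the documents do not give. Under independent days more than half survives. Nor does admitting "mild, moderate, and severe meth use disorder as determined by DSM-V-SCID criteria", where the pilot enrolled men without severe disorder, establish a ceiling: diagnostic severity is not days of use, and 75% positivity leaves room to fall.

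**Conclusion.** The justification is wrong as written. The pilot reductions of 18–22% are not similar to 32%, and at least the 0.78 is on another scale. A pilot-sized effect would probably not reach significance in Aim 1. The no-loss power of 35–48% at 54 participants (38–52% at 60) uses the documents' inputs and a variance model that reproduces their 24 points. The 15–30% range depends on the assumed independent days, 2–7 day window and 75% reference rate, and on both ratios being ratios of days.

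The missing day-count model is a specification gap, cheap to close. The choice of urine as primary outcome is not in question.

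**What to change.** 1. In Protocol 11.3 and the SAP, replace the similarity claim and the conclusion drawn from it with the actual figures: 18% (RR 0.82, intention-to-treat, not significant, with its unit stated) and 22% (RR 0.78, subgroup, meth-using days). Say that both are below the 32% detectable effect and that at least the 0.78 is not on the urine-positivity scale. The opening of 11.3, which claims 80% power for an 18–22% reduction, must be reconciled with this, as must the ~14.5-point sweat-patch figure at 80% retention in 8.13.
2. In 8.13, 11.3 and the SAP, prespecify meth-using days per week, from the timeline follow-back, as a supportive secondary outcome for Aim 1. Use the Poisson GEE with robust standard errors already planned for the Aim 2 counts, and keep urine primary.
3. State that a null urine result does not exclude a pilot-sized reduction in use.

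The cost is wording and one model on data already collected, with no new visits or participants. The published rationale becomes less favourable. The added outcome is self-reported and underpowered for RR 0.78–0.82, so it should be presented as an estimate with its interval and not as confirmation.

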Study Site: Study activities will take place at the Center on Substance Use and Health (CSUH) of the San Francisco Department of Public Health (SFDPH), a well-established clinical trial site located at [name]. [name] has a joint appointment as a Senior Research Scientist at SFDPH. He has conducted research at this field site since 2008. The site is centrally located near multiple transit lines with convenient access for residents of multiple neighborhoods with high rates of alcohol use. As noted above, we have had remarkable success recruiting and retaining meth users at this location. Study staff have access to both SFDPH resources (see LOS from SFDPH Director [name]) and UCSF resources as described in the Facilities section. The paired effort of these institutions has proven highly effective in both research and clinical care in San Francisco.

Randomization: Randomization (2:1 for ION versus placebo) will occur using double-blind, block randomization. *Assignment of two-thirds of participants to the ION arm was chosen to improve our ability to 1) examine whether EMI leads to greater ION adherence, and reductions in meth use, and 2) enhance our ability to detect adverse events in the active treatment arm.* This ratio was also selected with the knowledge that it has a negligible impact on the study's minimum detectable treatment effects, compared to a 1:1 allocation (i.e., the difference in the detectable treatment effects between the 1:1 and 2:1 allocation ratios were minor across all primary outcomes), while retaining a stable size for placebo, in the event that some participants are lost to follow-up. The study biostatistician will generate a random allocation sequence list with treatment assignments associated with order of enrollment, using randomly permuted blocks with randomly selected block sizes 3 and 6. To ensure balance by HIV-status, allocation will also be stratified by HIV serostatus. To mask the randomized allocation sequence, the statistician will provide this stratified list to the study pharmacist.

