Specific Aim 1: *To determine the efficacy of ION vs. placebo in reducing meth use, as determined by the proportion of meth-positive urine tests.* As in our prior trial, a GEE Poisson model with robust standard errors will be used to compare weekly urine test results by treatment assignment; this provides easier-to-interpret risk-ratios²¹⁸ rather than odds-ratios. The treatment effect of ION vs. placebo will be modeled as linearly increasing and summarized by the between-group difference in means at 12 weeks, net of any baseline difference. *Minimum Detectable Effects (MDEs) with sample size:* Based on the prior trial (93% retention with an 8-week follow-up), we estimate that 80% of participants will be retained at 12 weeks, and within-subject correlation will be 0.45. Under these assumptions, the study sample will have 80% power in 2-sided tests with a type-I error rate of 5% to detect net between-group differences in the reduction in sweat patch positivity of ~14.5 percentage points. In the Project iN study, we have observed reductions on meth use between 18%-22% among the ION arm, compared to placebo, in ITT and sub-group analyses.¹⁰⁹ Therefore, we believe that the reductions in meth use we are powered to detect in this aim are reasonable to anticipate. *In sensitivity analyses*, we will also evaluate between-group differences on changes in: 1) any meth-positive samples or self-report of meth use in timeline follow back; and 2) meth positivity from self-report only. Concordance of the urine testing, and self-reported measures will be examined using weighted Kappa and correlations. We recognize that meth use is a stigmatized behavior that may be underreported. Hence, in the event of discrepancies between urine results and timeline follow back data on meth use, we will treat the urine test results as the gold standard. *Additionally, we will analyze participant's perception of whether the EMI prompts had effects on various HBM constructs and explore whether these moderate treatment effects on meth use.*^{119,120}

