**MDEs:** Using data from our prior trial on baseline means, within-subject correlation, and over-dispersion, we estimate that the study sample of 54 participants will have 80% power to detect ~46% net reductions in the numbers of sexual partners and ~67% reductions in partners with whom meth is used. In our Project iN study, we have observed statistically significant reductions on sexual risk outcomes ranging between 85%-89% among the treatment arm, compared to placebo. Therefore, given the results from the prior trial, we believe that the reductions we are powered to detect in this aim are reasonable to anticipate.

**Specific Aim 3:** *To determine the efficacy of ION vs. placebo in increasing PrEP adherence among HIV-negative participants and ART adherence among participants living with HIV, as measured by serum drug levels and viral suppression rates.* We will use GEE Poisson models with robust standard errors to assess evidence that the intervention increases PrEP and ART adherence.

**MDEs:** Using the assumptions for loss to follow-up from Project iN for Aim 1, and informed by the within subject correlations of a PrEP adherence measure in the EPIC study and of detectable viral loads among HIV+ participants in a Mirtazapine trial for MSM who use meth, we estimate that the study sample of 54 participants will have 80% power to detect 10-19 percentage point increases in PrEP/ART adherence, depending on within-subject correlations and adherence levels in the reference group.

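### SAP Aim 2 names robust standard errors, but no small-sample method, for over-dispersed partner counts with only 18–20 placebo participants

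*SAP*

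**What the plan says.** SAP, Specific Aim 2: "We will use GEE Poisson models with robust standard errors to assess evidence that the intervention reduces HIV risk behaviors". The outcomes are the number of sex partners and the number of partners in meth use (below, meth-use partners). Neither the SAP nor Protocol 8.13 or 11.3 names a sandwich variant, a working correlation, a reference distribution or a randomization test.

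The detectable effects were obtained "Using data from our prior trial on baseline means, within-subject correlation, and over-dispersion", and the SAP concludes that "the study sample of 54 participants will have 80% power to detect ~46% net reductions in the numbers of sexual partners and ~67% reductions" for the second count. None of those inputs is printed. Under Aim 1, for urine results, the SAP states that "within-subject correlation will be 0.45" and sets a two-sided 5% level. Aim 2 repeats only the 80% power.

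Protocol 11.1 plans 40 participants on naltrexone and 20 on placebo; the SAP's 54 at 2:1 is 36 and 18. Retention is 90% in the SAP, but in Protocol 8.13 "we estimate that 80% of participants will be retained at 12 weeks". Protocol 8.11, Table 4, lists "Total # of sexual partners, by partner HIV status" among behavioral outcomes, at enrollment and months 1–3. The primary biologic outcome there is urine. Protocol 8.9 stratifies randomization by HIV serostatus, "using randomly permuted blocks with randomly selected block sizes 3 and 6".

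**The concern.** The sandwich variance is a large-sample estimate built from participant-level residuals. With 18–20 people in the smaller arm, each pulls that arm's fit toward himself, so residuals are too small and the standard error is biased low. Skewed counts make this worse, and a normal reference ignores the error in the variance estimate.

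The result would be p-values somewhat too small and intervals somewhat too narrow for one of the three efficacy aims. Because the SAP is silent, the choice between a corrected and an uncorrected test could also be made after the data are seen.

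**Working it through.** **Inputs from the documents.** 40:20 randomized; 36:18 for the detectable effects; 80% power and 5% two-sided (z sum 1.96 + 0.84 = 2.80); effects of 46% and 67%; four visits; serostatus strata; blocks of 3 and 6.

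**Assumed.** Correlation 0.45 (an Aim 1 figure); gamma-Poisson counts; the same four visits for meth-use partners; two equal strata; independence working correlation; z reference; dropout at random.

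**1. Standard errors implied by the stated effects.** The effects cannot be reproduced directly because their inputs are not printed. Back-solving SE = −ln(1 − reduction)/2.80:
- 46%: 0.616/2.80 = 0.220
- 67%: 1.109/2.80 = 0.396

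**2. Dispersion implied at correlation ρ.** With between-person gamma shape a, SE² = c(1/36 + 1/18)(1/ρ − 1)/a. Here c = 1.8 for a linear arm-by-time contrast over four visits and 4/3 for a constant one. At ρ = 0.45, 1/ρ − 1 = 1.222.
- Linear: 1.8 × 0.0833 × 1.222 = 0.1833. Then a = 0.1833/0.220² ≈ 3.79 (between-person CV 1/√a = 0.51) and 0.1833/0.396² ≈ 1.17 (CV 0.92).
- Constant: a = 2.81 (CV 0.60) and 0.87 (CV 1.07).

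So the 67% effect implies a much more dispersed count than the 46% effect. Two mean/dispersion splits fit each case: no visit-level dispersion (means 3.10 and 0.96 linear, 2.30 and 0.71 constant), or extra visit-level dispersion (means 6 and 3).

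**3. Null rejection, uncorrected sandwich with z.** 60 randomized, 10% monotone dropout, 5,000 trials per cell (Monte Carlo SE 0.3–0.45 points):

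| ρ = 0.45 | Total partners | Meth-use partners |
|---|---|---|
| Linear, no extra dispersion | 6.0% | 6.7% |
| Linear, extra | 6.8% | 8.5% |
| Constant, no extra | 7.0% | 7.5% |
| Constant, extra | 7.1% | 9.5% |

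False results favouring naltrexone are 2.8–4.1% and 3.4–4.6%, against a nominal 2.5%; those favouring placebo are about as frequent.

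**4. Sensitivity (total; meth-use partners).**
- 54 with complete data, linear: 6.8–7.7%; 7.9–9.7%.
- 20% dropout: 6.9–7.3%; 7.6–7.9%.
- ρ from 0.30 to 0.60: 6.0–7.6%; 6.4–11.3%. Only one setting passes 10%: ρ 0.60, constant contrast, extra dispersion.
- Lognormal instead of gamma heterogeneity, ρ 0.45: 7.5–7.7%; 7.8–9.0%.

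Every setting exceeds 5%. The mean robust SE is 3–6% too small for total partners and 5–16% for meth-use partners.

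**5. Coverage of nominal 95% intervals** (linear, ρ 0.45–0.60): 92.5–94.0% at a rate ratio of 0.54 and 90.8–92.9% at 0.33, short by 1.0–2.5 and 2.1–4.2 points.

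**6. Corrected test.** In a 2,000-trial repeat of the eight ρ = 0.45 cells, the uncorrected test rejected 6.5–7.6% and 6.8–9.8%. Mancl-DeRouen with t rejected 4.8–5.8% and 5.2–7.8%. Over the wider correlation range its worst setting for meth-use partners was 9.5%. A re-randomization test gave 4.8–5.7% in eight settings.

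**7. Power** (36:18 complete, linear, ρ 0.45). In one run it fell from 78.5% to 74.1% at the 46% effect (4.4 points) and from 77.5% to 72.7% at the 67% effect (4.8 points).

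**The case against.** **Silence is not a decision.** A reader might infer that the sponsor has chosen an uncorrected error. The SAP neither names nor excludes a correction, so the finding is that none is named. That is still a gap, since fixing the test in advance is the SAP's job.

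**The percentages are not document figures.** A reader might take 6–8% and 7–10% as the trial's actual error rates. The documents cannot support that: the prior-trial inputs are unseen, and 0.45 was stated for weekly urine results, not monthly partner counts. The direction held in every setting; the size is illustrative.

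**The calibration is approximate.** It uses null-level variance, although Poisson relative variance rises as the active-arm mean falls. Simulated uncorrected power scattered around 80%: about 76–83% at the 46% effect and 72–86% at the 67% effect, depending on the cell. The same effects are also printed for 60 participants in Protocol 8.13 and for 54 in the SAP. It would be too strong to say that the stated power is wrong by a known amount.

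**The consequence is limited.** The excess for total partners is small, and these counts are not the primary biologic outcome. This stands and keeps the point at moderate weight. Nothing here bears on the urine analysis.

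The time contrast, which the SAP writes only under Aim 1, is a separate matter; both forms were run above.

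**Conclusion.** The concern holds in a limited form. Aim 2 leaves the small-sample method open with 18–20 placebo participants; at the 80% retention in Protocol 8.13, week 12 would have about 16 (0.8 × 20). The usual sandwich with a normal reference would then be modestly anti-conservative: roughly 1–3 points above 5% for total partners and 2–5 points for meth-use partners at correlation 0.45. These sizes depend on the assumed count model, means and dispersion and on the borrowed correlation. The direction does not, over the range tried. The SAP should be changed, but this is no threat to the trial's main conclusion.

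**What to change.** In SAP Aim 2, replace the unspecified robust error with a Mancl-DeRouen bias-corrected sandwich and a t reference, taking participants minus mean-model parameters as degrees of freedom, for both tests and 95% intervals. With four mean parameters and 60 participants that is 56. State that results for meth-use partners remain approximate, because the correction reduces the excess there without fully removing it.

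For that count, a re-randomization p-value can be pre-specified as a supporting test, re-drawing assignments within the serostatus strata and the realised permuted blocks. With dropout it is valid only if assignment does not affect attendance, and the SAP should say so.

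The sponsor should recompute the 46% and 67% detectable effects from the prior-trial inputs using the corrected test, and print those inputs.

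The cost is a short SAP paragraph, with a correction available in standard GEE software; intervals about 6% wider (seen in three simulated data sets); and about 4–5 points less power at the stated effects. The optional test needs a short program and the existing allocation list. Sample size and trial conduct do not change.
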